9.7. Data management

For Phases 1 and 2, the Ontada study team will collaborate with Ontada's Commercial Intelligence group to collect the structured iKM data that will be used for analysis. The Commercial Intelligence team will be provided with a Data Collections Variable List, which will detail the specific data elements that will need to be included in the study dataset. A Data Analyst will begin by generating high-level study sample counts that demonstrate attrition rates of the inclusion/exclusion criteria.

The study team will review the attrition count and the Data Analyst will proceed with collecting the remaining data elements on the Data Collections Variable List. The Data Analyst will perform an initial quality control check of the study dataset before providing the file to the study team's Biostatistician on a secure server. Once received by the Biostatistician, data validation will continue and will consist of, but is not limited to, quality control checks for appropriate values, logical sequences and quantity of missing values.

During Phase 3, the Ontada Biostatistician will collect the structured iKM data that will be used for analysis. The biostatistician will begin by generating high-level study sample counts that demonstrate attrition rates of the inclusion/exclusion criteria. The study team will review the attrition count and the Biostatistician will proceed with collecting the remaining data elements detailed in the study protocol. The Biostatistician will perform data validation activities that will consist of, but are not limited to, quality control checks for appropriate values, logical sequences, and quantity of missing values.

For Phases 2 and 3, the Biostatistician will generate a list of patients eligible for chart review and will apply a sampling technique to identify the specific patients that will undergo chart review. This list of patients will then be securely transmitted to the Chart Review Team Manager. The chart review team consists of experienced oncology healthcare providers.

The Ontada study team will lead a training session with chart abstractors to discuss study specific considerations. Reference materials will also be provided to abstractors at this time. If chart abstractors have questions during the abstraction process, these will first be raised to the Chart Review Team Manager. If needed, questions can be escalated to the Outcomes Researcher and Principal Investigator.

Chart review will be accomplished by use of a secure, web-based eCRF. The main purpose of the eCRF is to obtain data required by this non-interventional study protocol in a complete, accurate, legible and in a timely manner.

The unstructured data will be linked to structured data, which will be converted to structured form by a computer using automated/algorithmic methods, such as natural language processing. Analyses will be conducted using SAS® (SAS Institute Inc., Cary, NC, US) and/or R: A Language and Environment for Statistical Computing (R Foundation for Statistical Computing, Vienna, Austria) as appropriate.

9.7.1. Case report forms (CRFs)/Data collection tools (DCTs)/Electronic data record

As used in this protocol, the term CRF should be understood to refer to either a paper form or an electronic data record or both, depending on the data collection method used in this study.

A completed CRF is required for each included patient. The completed original CRFs are the sole property of Pfizer and should not be made available in any form to third parties, except for authorized representatives of Pfizer or appropriate regulatory authorities, without written permission from Pfizer. The Ontada study team shall ensure that the CRFs are securely stored and will be password protected to prevent access by unauthorized third parties.

The Ontada study team has ultimate responsibility for the collection and reporting of all data entered on the CRFs as required and ensuring that they are accurate, authentic/original, attributable, complete, consistent, legible, timely (contemporaneous), enduring, and available when required. The CRF serves as the source document. Any corrections to entries made in the CRFs must be dated, initialed, and explained (if necessary) and should not obscure the original entry.

9.7.2. Record retention

To enable evaluations and/or inspections/audits from regulatory authorities or Pfizer, Ontada agrees to keep all study-related records, including the identity of all participating patients (sufficient information to link records, e.g., CRFs[/DCTs] and hospital records), copies of all CRFs[/DCTs], safety reporting forms, source documents, detailed records of treatment disposition, and adequate documentation of relevant correspondence (e.g., letters, meeting minutes, and telephone call reports). The records should be retained by Ontada according to local regulations or as specified in the Ontada contract whichever is longer. Ontada must ensure that the records continue to be stored securely for so long as they are retained.

If Ontada becomes unable for any reason to continue to retain study records for the required period, Pfizer should be prospectively notified. The study records must be transferred to a designee acceptable to Pfizer.

Study records must be kept for a minimum of 15 years after completion or discontinuation of the study, unless Ontada and Pfizer have expressly agreed to a different period of retention

via a separate written agreement. Record must be retained for longer than 15 years if required by applicable local regulations.

Ontada must obtain Pfizer's written permission before disposing of any records, even if retention requirements have been met.

9.8. Data analysis

As the foreseen analyses are defined in enough detail in this protocol, no further statistical analysis plan will be developed.

9.8.1. Analysis sets

Phases 1 and 2

For analyses performed to meet the Phase 1 objectives, all patients who the meet the eligibility criteria defined in Section 9.3.1 will be considered. The study cohorts will be identified based on subsequent therapy following alectinib. For these analyses, datasets consisting of the structured data elements, plus the LADMF to confirm vitality status, required for the landscape analyses will be constructed.

The Phase 2 (chart review) analyses will be limited to a sample of 100 qualified front-line alectinib patient charts identified from Phase 1. The chart review analysis sets will be constructed from both structured and unstructured data, with the LADMF used to confirm vitality status.

Phase 3

For analyses performed to meet the Phase 3 unstructured objectives, all patients who the meet the eligibility criteria defined in Section 9.3.1 will be considered. The study cohorts will be identified based on subsequent therapy following alectinib. For these analyses, datasets consisting of the structured data elements, plus the LADMF to confirm vitality status, required for the landscape analyses will be constructed.

Phase 3 chart review analyses will include a subset of patients from Phase 2 chart review who had ongoing treatment at the end of the observation period and an additional sample of 100 qualified front-line alectinib patients from Phase 3. The chart review analysis sets will be constructed from both structured and unstructured data, with the LADMF used to confirm vitality status.

Some data elements will be captured with both structured and unstructured data. Since the chart review data are expected to provide a richer source of information, if data are available from both sources for a single patient, then chart review data will supersede what is available in the structured iKM data for the final analysis. To account for this, a final analysis data set will be constructed and used to update the landscape analyses once chart review data are available.

For Phase 3 exploratory analysis, all patients who meet the eligibility criteria defined in Section 9.3.2 will be considered. The study cohorts will be identified based on subsequent therapy following lorlatinib. For these analyses, datasets consisting of the structured data elements will be constructed.

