9.2. Study Design Phase 3 (study refresh and exploratory analysis)

During the Phase 3 data refresh, patients who have evidence of receiving alectinib during 01 June 2017 and 31 August 2020 will be eligible for inclusion in the study. Patients will be followed longitudinally until 31 August 2021, last patient record or date of death, whichever occurs first.

An overview of the study design for Phase 3 is presented in Figure 2.

Figure 2. Phase 3 data refresh study design

^{*}Last visit = last physical encounter, X = Additional visit or record of death

Phase 3 structured data objectives will be assessed among patients who meet study eligibility criteria as specified in 9.3.1 and stratified by subsequent treatment following alectinib.

Cohort A: All alectinib treated patients (overall population)

Cohort B (Alectinib only cohort): Alectinib treatment ongoing, or discontinued and no subsequent treatment³

Cohort C: Alectinib followed by treatment X (top 3 most frequent)

Cohort D: Alectinib followed by treatment Y (top 3 most frequent)

Cohort E: Alectinib followed by treatment Z (top 3 most frequent)

[figure not shown]
³ Patients with ongoing alectibin treatment, patients who discontinued alectinib and patients who did not have a subsequent treatment may be analyzed as separate cohorts depending on sample size of patients

Two groups of patients are planned for chart review during Phase 3. The first group includes patients from Phase 2 chart review who had ongoing treatment at the end of the observation period (31 December 2019). These patients will undergo additional follow-up through 31 August 2021.

An additional sample of approximately 100 patients who meet the Phase 3 eligibility criteria and received alectinib as front-line therapy and received subsequent treatment among the following groups will also undergo chart review:

- Alectinib → lorlatinib
- Alectinib → crizotinib
- Alectinib → brigatinib
- Alectinib only
- Alectinib → chemotherapy (optional)

Figure 3. Phase 3 exploratory analysis study design

^{*}Last visit = last physical encounter, X = Additional visit or record of death

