9.3.4.2. Chart review for Phase 3 study refresh

Two groups of patients are planned for chart review during Phase 3. The first group includes patients from Phase 2 chart review who had ongoing treatment at the end of the observation period (31 December 2019). These patients will undergo additional follow-up through 31 August 2021.

An additional sample of approximately 100 patients who meet the Phase 3 eligibility criteria and received alectinib as front-line therapy and received subsequent treatment among the following groups will undergo chart review:

- Alectinib → lorlatinib
- Alectinib → crizotinib
- Alectinib → brigatinib
- Alectinib only
- Alectinib \rightarrow chemotherapy (optional)

In the event the total number of eligible patients following structured data screening exceeds the planned number of charts for review, a random sample will be selected.

During the course of abstraction, patients' eligibility for the study will be verified and some of these patients may be found to be ineligible. A total of up to 125 charts are assumed to be reviewed to identify at least 100 patients who received post-alectinib treatment from the above listed priority groups.

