9.6. Study size

A preliminary feasibility assessment for Phases 1 and 2 identified 293 patients who were treated with alectinib after 01 November 2017, with approximately half treated in the front-line setting. Of the 293 patients receiving alectinib, 74% (n=217) patients had an ALK result. Approximately 20-30% of the 293 patients received a subsequent therapy after alectinib. It is estimated that approximately 300 patients will be included in the Phase 2 structured data analysis. Targeted chart review for Phase 2 is proposed to occur on 150 patients receiving alectinib to identify at least 100 patients who received alectinib as front-line. In the event the total number of eligible patients following structured data screening exceeds the planned number of charts for review, a random sample will be selected.

For Phase 3 structured analysis, a preliminary feasibility assessment identified 521 patients who were treated with alectinib from 01 June 1 2017 through 31 December 2020. Chart review for Phase 3 will include patients who had ongoing treatment at the end of Phase 2

study period, and an additional 125 patients will be targeted to identify 100 new patient who received alectinib as front-line therapy. For Phase 3 exploratory analysis, a preliminary feasibility assessment identified 134 patients who were treated with lorlatinib from 01 November 2018 through 31 December 31 2020.

The final study population for analysis will be defined after identification and review of the patient population meeting the eligibility criteria in the iKM database. A specific power calculation will not be performed as this is a descriptive analysis.

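### Section 9.8.1 does not settle whether Phase 2 chart patients who had stopped treatment or died stay in the Phase 3 chart-review set; read literally, it leaves out the early failures

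*Combined protocol and SAP*

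**What the plan says.** Section 9.8.1 defines who is analysed. For Phase 2: "The Phase 2 (chart review) analyses will be limited to a sample of 100 qualified front-line alectinib patient charts". For Phase 3 it makes two statements.

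- The first reads "For analyses performed to meet the Phase 3 unstructured objectives, all patients who the meet the eligibility criteria" of Section 9.3.1. It then describes structured landscape datasets, so the word unstructured may be a slip.
- The second reads "Phase 3 chart review analyses will include a subset of patients from Phase 2 chart review who had ongoing treatment", judged at the Phase 2 cut-off, together with 100 further front-line patients.

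Section 9.2 says "Two groups of patients are planned for chart review during Phase 3". Section 9.3.4.2 repeats this and adds "The first group includes patients from Phase 2 chart review who had ongoing treatment at the end of the observation period (31 December 2019"), with follow-up to 31 August 2021. The second group is about 100 new front-line patients from a list of treatment groups, one of which is alectinib only.

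Other text bears on the question:

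- Section 8 updates the Phase 1 and Phase 2 objectives with longer follow-up.
- Section 9.3.3 replicates the earlier stratifications for all eligible patients.
- Section 9.5 merges every source into a single dataset, and Section 9.8.1 gives chart data precedence over structured data.
- Section 9.8.3 times OS, DOT and PFS from alectinib start and provides no delayed entry.
- Table 1 takes progression dates and discontinuation reasons from chart review only.
- Section 9.8 says that there will be no separate SAP.

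**The concern.** Two competent programmers could build different Phase 3 chart-review datasets from this text. One would keep all 100 Phase 2 charts and add the new ones. The other would keep only the Phase 2 charts with ongoing treatment and add the new ones.

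The second dataset omits the Phase 2 patients who failed early. Those it carries forward could not have died or left treatment before 31 December 2019, yet their time since alectinib start counts as ordinary time at risk. The pooled chart-review estimates are then partly conditioned on survival and continued treatment. Objectives 8 and 9 are most exposed, because the structured analysis has neither discontinuation reasons nor progression dates with which to repair the loss. It is also undefined whether ongoing treatment means alectinib or any therapy.

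**Working it through.** The plan states no figure on this point to reproduce; Section 9.6 waives a power calculation. The check is date arithmetic followed by an illustration.

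**1. Time guaranteed by selection.** Phase 2 index dates run from 1 June 2017 to 30 June 2019 (Section 9.3). To 31 December 2019 that is 184/30.4375 = 6.0 months for the latest start and 943/30.4375 = 31.0 months for the earliest.

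**2. Share carried forward.** Assume uniform starts over 25 months, exponential time on alectinib with rate λ = ln 2/median, and ongoing meaning on alectinib. The share is [exp(−6λ) − exp(−31λ)]/(25λ). With a median of 25.7 months (the trial PFS in Section 7, borrowed here as a DOT), λ = 0.02697 and the share is (0.8506 − 0.4334)/0.6743 = 0.62. The two-group set then holds about 162 patients instead of 200.

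**3. Early part of the curve.** No carried-forward patient can stop before month 6. The pooled share still on treatment at 6 months is (100 × 0.851 + 62)/162 = 0.908, against a true 0.851. By simulation, the 24-month share is 0.64 against 0.52.

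**4. Median DOT, new charts drawn at random.** Kaplan-Meier on large simulated samples weighted to 100 Phase 2 and 100 new charts, data cut at month 51, no loss to follow-up. Section 9.6 reports that "a preliminary feasibility assessment identified 521 patients who were treated with alectinib"; if half are front-line, 521/2 ≈ 260, less 100 already charted leaves about 160. Two pools were used: (A) starts uniform over 39 months; (B) 47 of the 160 from the first 25 months (293/2 less 100) and 113 from the last 14.

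| True median (months) | Carried forward | Two-group set | All Phase 2 charts kept |
|---|---|---|---|
| 18 | 51% | about 25 | 18.0 |
| 25.7 | 62% | about 34 | 25.7 |
| 36 | 71% | about 45 | 36.0 |

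**5. Median DOT, new charts enriched for patients who left alectinib.** With a true median of 25.7, the two-group median is 29.5–32.1 if 60% of new charts have discontinued, 25.8–28.6 at 70% and about 24–27 at 75%. It is 23.3 at 88%, which pool A can supply. With a true median of 18 it can fall to 15.5–16.9 when 94–100% have discontinued. The direction is then undetermined.

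**6. OS at 24 months, new charts drawn at random.** Assume that 10% of treatment ends are deaths and that survival after stopping is exponential.

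| Median on alectinib | Median after stopping | Two-group set | All kept |
|---|---|---|---|
| 15 | 12 | 0.71 | 0.62 |
| 20 | 12 | 0.77 | 0.69 |
| 25.7 | 12 | 0.82 | 0.74 |
| 15 | 24 | 0.80 | 0.74 |
| 20 | 24 | 0.85 | 0.79 |
| 25.7 | 24 | 0.88 | 0.82 |

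A second set of scenarios, with explicit switching and both meanings of ongoing, gave an excess of 6.6 to 9.5 points. Together, roughly 5 to 10 points.

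**7. Discontinuation reasons (true median 25.7).** Stops in omitted Phase 2 charts: 100 − 62 = 38. Later stops in carried-forward charts: 62 × [1 − exp(−20λ)] = 62 × 0.417 = 26. Stops in new charts: 55 (A) or 47 (B). The omitted share is 38/119 = 32% or 38/111 = 34%; it is 30–36% across medians of 18 to 36.

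**The case against.** The strongest reply is that nothing is discarded. Sections 9.2 and 9.3.4.2 describe who is planned for review and gets more follow-up, which is an abstraction plan. Phase 2 analyses are limited to their charts, whereas Phase 3 analyses only include the two groups. With Sections 8, 9.3.3 and 9.5 and the precedence given to chart data, keeping charts already held is at least as natural a reading. That stands, and it makes the bias conditional. It does not remove the ambiguity, because the section that defines the analysis sets names only the two groups.

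Three stronger readings are tempting but not supported.

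- A reader might infer that the whole Phase 3 chart-review set is conditioned on survival to 31 December 2019. Only the carried-forward patients are, about 62 of 162 in the example. New charts come from the full identification window and need not be alive on that date.
- A reader might infer that the bias is always upward. That holds in the random-draw scenarios computed; with enrichment the DOT error can reverse.
- A reader might infer a quota of treated patients from "A total of up to 125 charts are assumed to be reviewed to identify at least 100 patients who received post-alectinib treatment". The sentence goes on to refer to the listed priority groups, which include alectinib only; Section 9.6 targets 100 new front-line patients; and Section 9.3.4.2 provides for random sampling when eligible patients exceed the planned charts. The documents do not fix unequal sampling by group.

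It is also fair that the study is descriptive, that chart-review PFS and OS by cohort depend on the final sample size, and that reasons for stops before 2020 belong to the Phase 2 report.

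**Conclusion.** The point holds as an unsettled analysis set with a material consequence under the literal reading; it should be fixed. It is not shown that the sponsor intends to drop these patients.

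If the two-group set is used with randomly drawn new charts, pooled median DOT is overstated by about 7 to 9 months and 24-month OS by roughly 5 to 10 points. About a third of discontinuation reasons would be absent from the refreshed objective 8 result. These sizes rest on exponential times, uniform entry and no loss to follow-up; the DOT figures also take ongoing to mean on alectinib. They are illustrations, not estimates. No size is claimed for PFS: it was not computed, and being on treatment does not select directly on being progression-free. Structured-data Phase 3 DOT and OS use all eligible patients and are not affected.

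**What to change.** 1. In Sections 9.8.1 and 9.3.4.2, state that all Phase 2 chart-review patients remain in the Phase 3 chart-review analysis set, and that ongoing treatment at 31 December 2019 determines only whose chart is re-abstracted.
2. Define ongoing treatment as alectinib or any therapy, and correct unstructured in the opening Phase 3 sentence of Section 9.8.1 if structured is meant.
3. For Phase 2 patients whose charts are not reopened, update OS and later treatments from the planned structured and LADMF extract. For PFS, censor those without recorded progression at their last Phase 2 chart visit.
4. Only if new charts are in fact drawn at unequal rates by subsequent-treatment group, report them within group or weight overall estimates by the inverse sampling fraction. Keeping all Phase 2 charts would not cure this alone: with 75% discontinuers unweighted, a true DOT median of 25.7 reads 18.4–20.7; weighted, it reads 25.6.

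The cost of items 1 to 3 is a few sentences, one definition and dataset construction; the Phase 2 chart data are held and the structured data are re-extracted anyway. Within-group reporting costs nothing. Weighting needs the group counts from the structured screen and, in the cases examined, leaves an effective 70 to 92 of the 100 new charts. With the 100 Phase 2 charts, overall confidence intervals widen by a factor of √(200/192) to √(200/170), roughly 2 to 9%.

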9.3.4. Chart review selection

9.3.4.1. Chart review for Phase 2

Among patients who meet the eligibility criteria defined by the inclusion/exclusion criteria listed in Section 9.3.1, a sample size of approximately 100 qualified front-line alectinib patient charts will be selected to undergo a targeted chart review. In the event the total number of eligible patients following structured data screening exceeds the planned number of charts for review, a random sample will be selected.

During the course of abstraction, patients' eligibility for the study will be verified and some of these patients may be found to be ineligible. A total of up to 150 charts are assumed to be reviewed to identify at least 100 patients who received alectinib as front-line.

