9.8.3. Statistical methods

Description of study enrollment

To be included in the study patients must meet each of the inclusion criteria and none of the exclusion criteria listed in Section 9.3.1. Counts of patients excluded for each criterion will be summarized.

Additionally, the counts of patients to be classified into the following subgroups will be presented⁵:

- Cohort A: All alectinib treated patients (overall population)
- Cohort B (Alectinib only cohort): Alectinib treatment ongoing, or discontinued and no subsequent treatment⁶
- Cohort C: Alectinib followed by treatment X (top 3 most frequent)
- Cohort D: Alectinib followed by treatment Y (top 3 most frequent)
- Cohort E: Alectinib followed by treatment Z (top 3 most frequent)

Description of patient demographic, clinical and treatment characteristics

Descriptive analyses will be conducted to evaluate the demographic, clinical and treatment characteristics overall, as well as for each of the study cohorts. Results will be reported in

⁵ Final cohorts will be decided upon sample size. Patients receiving chemotherapy after initiating alectinib will be included in the patient sample

⁶ Patients with ongoing alectibin treatment, patients who discontinued alectinib and patients who did not have a subsequent treatment may be analyzed as separate cohorts depending on sample size of patients

aggregate. Categorical variables (e.g., ECOG performance status) will be reported as frequency and percentage. Continuous variables such as age will be reported as mean, standard deviation, median and range (minimum-maximum). In the case of missing observations, the number and percentage of missing values will be reported.

For comparative analysis, i.e. comparing 2 or more treatment groups (e.g., ALK inhibitor sequences) or strata (front-line alectinib and non front-line alectinib), statistical significance will be reported with level of statistical significance based on p = 0.05 level as well as 95% confidence intervals.

Chi-square testing will be used to assess associations between categorical variables when patient counts for single cells within the results tables are greater or equal to 5. When distribution cannot be assumed to be Chi-square, then Fisher's exact test will be used. Depending on normality, Analysis of variance (ANOVA)/t-tests or Kruskall-Wallis tests will be used for continuous variables. An alpha level of 0.05 will be the primary criterion for statistical significance of this study.

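### Chart values replace structured values mainly in front-line patients, so front-line versus non-front-line comparisons of dual-source items partly reflect data source

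*Combined protocol and SAP*

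**What the plan says.** The rule is in section 9.8.1. Where both sources hold a value, "chart review data will supersede what is available in the structured iKM data for the final analysis". It adds that "a final analysis data set will be constructed and used to update the landscape analyses once chart review data are available". Section 8 defines the landscape population as patients given alectinib in any line.

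Chart review is narrower. Section 9.8.1 says: "The Phase 2 (chart review) analyses will be limited to a sample of 100 qualified front-line alectinib patient charts identified from Phase 1". For Phase 3 it adds "an additional sample of 100 qualified front-line alectinib patients from Phase 3", together with Phase 2 chart patients still on treatment at the end of 2019, who come from the same front-line sample.

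Section 9.8.3 then compares the two groups. For treatment groups or "strata (front-line alectinib and non front-line alectinib), statistical significance will be reported" at the 0.05 level with 95% confidence intervals. Descriptive tables and the clinical outcomes are also to be split by front-line status, subject to sample size. Table 1 in section 9.4 lists structured data plus chart review as the source for treatment dates, subsequent treatment, duration of therapy (DOT), ALK status, metastatic sites, front-line status and, together with LADMF, death.

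**The concern.** A comparison of two strata assumes that an item is measured in the same way in both. Here one stratum would be largely chart-corrected and the other essentially structured-only. The protocol itself expects the sources to differ: it calls the chart the richer source, uses chart review to confirm oral ALK inhibitor data, and says in section 9.10.1 that drugs from unaffiliated pharmacies are not captured and that earlier treatment may be recorded only in progress notes.

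Any such difference in capture or dates would enter the contrast between strata and be tested at 0.05. The plan has no source indicator and no structured-only sensitivity analysis, and section 9.10 does not list mixed source as a limitation. Section 9.8 rules out a separate analysis plan that could settle it later.

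**Working it through.** **Inputs from the documents (section 9.6 unless stated).** Phase 1/2 feasibility "identified 293 patients who were treated with alectinib after 01 November 2017, with approximately half treated in the front-line setting". Phase 3 feasibility "identified 521 patients who were treated with alectinib"; its front-line share is not given. An ALK result was available for 217 of 293. Subsequent therapy was 20-30%. Qualified charts: 100 in Phase 2 and 100 new in Phase 3 (section 9.8.1). On charts opened, section 9.3.4.1 says: "A total of up to 150 charts are assumed to be reviewed to identify at least 100 patients who received alectinib as front-line"; section 9.3.4.2 allows up to 125 for 100 in Phase 3.

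**The plan's own figure.** 217/293 = 74.1%, which agrees with the stated 74%. No power or sample size is derived, so none can be checked.

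**Chart share by stratum** = qualified charts / (N × front-line share). The share is taken as 50%, with 45-55% as an assumed range.

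- Phase 2: 293 × 0.5 = 146.5; 100/146.5 = 68% (62-76%).
- Phase 3, all Phase 2 chart data retained: 521 × 0.5 = 260.5; 200/260.5 = 77% (70-85%).
- Phase 3, only the new charts counted: 100/260.5 = 38%.
- Non-front-line: 0% by design. If every chart opened but not qualified were non-front-line and kept, at most 50/146.5 = 34% in Phase 2 and (50 + 25)/260.5 = 29% in Phase 3.

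The 521 count runs to 31 December 2020, past the 31 August 2020 identification cut-off, so the true Phase 3 denominator may be smaller and the share higher.

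**What an imbalance of this size could do.** These are illustrations only. The strata are taken as truly identical, tests as two-sided at 0.05, chart share as 68% (N = 293) or 77% (N = 521), and non-front-line as uncharted. The chart gains are assumptions, because the documents give none.

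- *ALK result recorded.* Front-line proportion = 0.74 + share × (chart capture − 0.74). With chart capture of 80-100%, front-line shows 78-92% against 74% at N = 293, and a spurious p < 0.05 arises in 13-98% of studies. At N = 521 it shows 79-94%, and the rate is 23% to nearly 100%.
- *Subsequent therapy.* Front-line proportion = p + share × gain, with p = 20-30% and a gain of 5-15 points. Spurious significance arises in 9-52% of studies at N = 293 and 15-85% at N = 521.
- *DOT.* Log-rank simulation with 1,000 replicates, exponential times with an 18-month median, uniform censoring at 6-31 months (N = 293) or 12-51 months (N = 521), and charted times multiplied by 0.8 to 1.25. Rejection is about 6-16% at N = 293 and 10-36% at N = 521. With one source throughout it is 6.2% and 5.8% (Monte Carlo error about 0.7 points), close to nominal.

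The width of these ranges shows that the effect could be negligible or large.

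**The case against.** The strongest reply is that the comparison is peripheral. No numbered objective contrasts front-line with non-front-line; the objectives stratify by subsequent treatment. The split is conditional on sample size and the study is descriptive. That limits the importance of the point, but section 9.8.3 still names these strata for testing.

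A second reply is that structured-plus-LADMF data sets are already built and Phase 1 has an interim report from structured data. This stands for the first round. In Phase 3, however, section 9.8.4 places the analyses after chart review, and section 9.8.1 has the merged file update the landscape results. Reported missing percentages would expose differences in completeness, but not missed events or shifted dates.

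Several stronger readings are tempting, and the documents do not support them:

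- *A quantified false survival gap.* Assuming 66% survival at 24 months, 5-10 points of death capture recovered by charts and 80% of patients charted gives 0.34 × (0.05 to 0.10) × 0.8 = 1.4-2.7 points. None of those inputs is in the protocol. Survival is also the least exposed outcome: LADMF linkage is planned in both strata and its date has priority, and Phase 2 chart patients who had stopped treatment get no further chart follow-up. With 260 per stratum and no censoring, the standard error of the difference is √(2 × 0.66 × 0.34/260) = 4.2 points, well above that gap.
- *Chart data in no non-front-line patient.* This is the design intent, but non-qualifying charts may be opened and the overwrite rule, read literally, covers them.
- *Ineligible patients dropped from the front-line stratum alone.* Section 9.3.4 says that abstraction may find patients ineligible. It does not say that they leave the landscape population.
- *Complete confounding.* Part of the front-line stratum stays structured-only, and structured-only fields such as age, race, ECOG, smoking and histology are unaffected.

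A fair caution also applies to the remedy. Front-line status is itself dual-source, and structured data may label pretreated patients as front-line. A structured-only comparison keeps that misclassification.

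**Conclusion.** The concern holds in a limited form. Followed as written, the plan measures dual-source items differently in the two strata: about 68% of front-line patients carry chart values in Phase 2 and at most about 77% in Phase 3, against few or no non-front-line patients. These shares assume that half of patients are front-line; the 77% also assumes that all Phase 2 chart data are retained. The affected items are treatment dates, DOT, subsequent treatment, ALK status, metastatic sites and, to a lesser degree, deaths. Front-line classification is exposed too: charts can move apparent front-line patients out of the stratum, but no apparent non-front-line charts are sampled to move patients in.

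The documents give neither the direction nor the size of the bias. The rejection rates above show only that modest assumed chart gains can matter. The point applies only if the stratified analyses are run. It is a worthwhile, inexpensive improvement and not a fault in the main objectives.

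**What to change.** In sections 9.8.1 and 9.8.3, state that front-line versus non-front-line comparisons of dual-source items will be run on structured plus LADMF data for all patients and reported beside the chart-updated tables. Base any between-stratum p-value on the single-source version. Keep chart-superseded data for the chart-review objectives. State whether data from charts that are opened but do not qualify enter the merged file.

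Progression date and reason for discontinuation come only from charts, so they have no single-source counterpart and this change does not cover them.

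The cost is one extra table run from data already held. The downside is that the single-source version does not use chart corrections, including correction of front-line status. For that reason both versions should be shown.
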